All analyses will be conducted in consultation with [name], the study biostatistician. Descriptive analyses and graphic displays will be used to identify outliers, missing data and patterns of attrition that will guide decisions about the use of transformations and appropriate tests. Demographic variables and baseline measures will be compared between the GLB+10TC and GLB+NC conditions. In all outcome analyses we will use an intent-to-treat (ITT) approach in which participants remain in the study arm to which they are randomized regardless of attrition. The primary analytic strategy will be a mixed models approach in which treatment group, time, and time by group interaction are treated as fixed effects, and subject and percent weight loss during the first phase of intervention (<3.5% and >3.5%) are treated as a random effects to account for individual subject variability. Hypothesis tests will be two-sided and significance will be set at the 0.05 level. Analytical tools will include SAS (SAS Institute, Inc., Cary NC), Stata (StatCorp LP, College Station, TX) and StatXact (Cytel, Inc. Cambridge, MA). Mixed models are applicable to longitudinal datasets that contain missing observations, with

the assumption that the data are considered to be missing at random (MAR) or ignorable missing. Although we will be proactive in maximizing subject retention, we anticipate 75% adherence over the 12-month intervention period. Those who drop out or are lost to follow-up will be compared to those who have completed intervention sessions and research assessments using standard parametric and non-parametric methods, as appropriate. We will examine the patterns of missingness and, if necessary, account for missingness in outcome analysis (e.g., the covariate approach). Finally, regression modeling will be conducted to adjust for covariates, including demographic variables such as age, race, sex, number of sessions completed, as well as any other variables that have been found to differ across treatment conditions at baseline.

Research Questions

Hypothesis 1 (feasibility): On average, we will enroll ≥ 107 participants per year for each of three years to GLB-12; they will complete $> 65\%$ of sessions, return $\geq 50\%$ of self-monitoring records and report above average program satisfaction at the 4-month assessment.

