Analysis Plan: The overall approach will be to report descriptive statistics, including the total number of participants enrolled, the distribution of the number of GLB-12 sessions completed, the percentage of participants completing 8 (65%) or more sessions (the definition for acceptable attendance), the percentage of participants who return six (50%) or more of the self monitoring records (the definition for acceptable behavioral adherence) and the distribution of program satisfaction ratings. Summary descriptive statistics will include mean, median, standard deviation and confidence intervals for continuous variables and proportions, ranges and percentiles for categorical variables.

Hypothesis 2 (effectiveness): On average, participants will achieve $\geq 5\%$ weight loss (the definition of acceptable weight outcome in prevention programs) and ≥ 150 minutes of self reported moderately vigorous physical activity minutes per week (the recommended level in prevention programs), and show corresponding waist, glucose, blood pressure and lipid improvements (adjusted for medication use).

Analysis Plan: For the weight measure, we will examine both absolute weight change (kg) and percent weight change pre to post-intervention (0-4 months). Student t-test and Chi-Square statistics will be used to assess the absolute and percent weight change outcomes, respectively. We will also use descriptive statistics to identify the proportion of total participants achieving $\geq 5\%$ weight loss and the proportion achieving ≥ 150 minutes. Similarly, Student t-tests will also be used to assess pre to post intervention changes in waist, glucose, lipid, and blood pressure measures. Because we know that medications will effect these outcomes we will conduct separate sub-group analyses for lipid endpoints to control for statin use, and for blood pressure endpoints to control for blood pressure medication use.

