Power and Sample Size Considerations: The primary endpoint of this investigation is defined as the proportion of participants, in each intervention arm, who maintain the designated target weight loss of $\geq 5\%$ at 12 months from baseline. Additional power calculations were derived for the changes in absolute weight loss from 0-12 months and in fasting glucose levels from 0-12 months. For our primary endpoint of $\geq 5\%$ weight loss at 12 months, with $N = 160$ in each arm and assuming no more than 25% attrition, we have 80% power to detect differences of 19% between the two intervention conditions in the proportion of subjects achieving this weight loss target. There is 90% power to detect differences of 21% between the two groups. This translates to roughly half or more of the participants in the telephonic continued contact group maintaining $\geq 5\%$ weight loss compared to only about one-third of those in the newsletter control condition. These estimates are based on a Fisher's Exact test conducted at $\alpha = 0.05$ two sided with $N = 120$ in each arm. In addition, we also calculated power estimates for various differences in absolute weight loss (lbs) between GLB + 10TC and GLB + NC based on previous GLB outcomes presented in Table 2 (23). Assuming a two sample t-test conducted at $\alpha = 0.05$ two-sided with a standard deviation of 10.5 we find that there is 80% power to detect group differences of 3.8 lbs or 90% power to detect group differences of 4.4 lbs between the two arms at 12 months. Finally, for the secondary endpoint analysis of differences between GLB + 10TC and GLB + NC in fasting plasma glucose changes from 0-12 months and assuming a two sample t-test conducted at $\alpha = 0.05$ two-sided with a standard deviation of 11.9 based on data presented in Table 2 (23), we project that there will be 80% power to detect a difference of ≥ 4.3 mg/dl decrease or 90% power to detect a difference of ≥ 5.0 mg/dl decrease between the two intervention arms.

Hypothesis 3: GLB+10TC will be associated with more favorable weight, waist, glucose, lipid, blood pressure gait speed, grip strength, balance and HRQL (based on the physical component summary and the mental component summary scores from the SF-12v2®) compared to the GLB + NC group at 12- and 24-month follow up assessments.

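### The trial is sized on the proportion with at least 5% weight loss at 12 months, but the analysis text does not declare that comparison as primary or say how a missing month-12 weight counts

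*Combined protocol and SAP*

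**What the plan says.** **Endpoint and sizing.** The power text in section 2.18, repeated in section 3.12, states: "The primary endpoint of this investigation is defined as the proportion of participants, in each intervention arm, who maintain the designated target weight loss" of at least 5% at 12 months from baseline. It assumes 160 per arm and at most 25% attrition. It claims 80% power for a 19-point difference and 90% for 21 points, with about one-third succeeding under newsletters. "These estimates are based on a Fisher's Exact test conducted at" two-sided 0.05 with 120 per arm.

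**Analysis.** The opening of section 2.18 says: "The primary analytic strategy will be a mixed models approach in which treatment group, time, and time by group interaction" are fixed effects. The Hypothesis 3 Analysis Plan, which covers the randomized comparison of outcomes, applies a repeated measures mixed model to absolute and percent weight loss and to the other outcome measures. Its planned contrasts are on percent weight loss at 12 and 24 months.

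**Where the 5% threshold is analyzed.** It appears only in the Hypothesis 2 plan for months 0 to 4: "We will also use descriptive statistics to identify the proportion of total participants achieving" the target. That plan also says: "Student t-test and Chi-Square statistics will be used to assess the absolute and percent weight change outcomes, respectively". Both sentences concern pre-to-post change in the whole cohort, before the randomized phase.

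**Missing data.** Section 2.18 says "we will use an intent-to-treat (ITT) approach in which participants remain in the study arm to which they are randomized" regardless of attrition. It states missing at random as the assumption of the mixed models, plans a comparison of dropouts with completers, and adds: "We will examine the patterns of missingness and, if necessary, account for missingness in outcome analysis", with a covariate approach as the example.

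**The concern.** A primary analysis should test the endpoint that the trial declares and is sized on. Here the endpoint is a proportion and the strategy called primary models mean change. An analyst following the Hypothesis 3 plan would report a contrast in mean percent weight loss as the main result. An analyst following the power text would report Fisher's exact test on the proportions. These can give different answers, and the plan does not say which one decides.

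The second gap is the status of participants without a month-12 weight. At 25% attrition that is up to 80 of 320. The intention-to-treat sentence suggests a denominator of 160 per arm and the power text uses 120. Missing at random in a model for continuous weight does not by itself assign anyone a yes or a no. The choice changes the effect being estimated, the power and possibly the conclusion.

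**Working it through.** **Inputs from the documents:** 160 per arm; 25% attrition; two-sided alpha 0.05; newsletter rate about one-third; differences of 19 and 21 points; weight difference of 3.8 lb with SD 10.5. Fisher power below is exact, by full enumeration of both binomials.

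**1. The plan's own figures.** 160 × 0.75 = 120 per arm.
- 33.3% v 52.3%: power 81.8% (stated 80%).
- 33.3% v 54.3%: power 88.7% (stated 90%).
- 3.8 lb, SD 10.5, t-test, 120 per arm: 79.7% (stated 80%).

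These reproduce and are not criticized.

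**2. Mean or proportion as primary.** Assume that weight loss is normal with equal SDs, and that the same standardized shift applies to percent loss.
- Shift = 3.8 / 10.5 = 0.362 SD.
- Telephone rate = Φ(Φ⁻¹(1/3) + 0.362) = Φ(−0.431 + 0.362) = 0.473.
- Difference = 0.473 − 0.333 = 13.9 points.
- Power, 120 per arm: t-test 79.7%, Fisher 55.5%.
- In the other direction, 19 points corresponds to 0.489 SD: t-test 96.5%, Fisher 81.8%.

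**3. Missing-status rule at the plan's 25% in each arm.** Completer rates are 33.3% and 52.3%.
- Observed cases, 120 per arm: power 81.8%.
- Missing = not achieved, 160 per arm: 0.75 × 33.3% = 25.0% and 0.75 × 52.3% = 39.3%, a difference of 14.3 points; power 74.8%.

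Illustrative counts of 56 v 40 participants reaching the target:
- 56/120 v 40/120: 13.3 points, Fisher p = 0.048.
- 56/160 v 40/160: 10.0 points, Fisher p = 0.067.

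**4. Unequal attrition, illustration only.** The documents give 25% and no split by arm. The splits below are assumed, under missing = not achieved, 160 per arm.

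| Newsletter / telephone missing | Completer rates | Rates analyzed (newsletter v telephone) | Rejection |
|---|---|---|---|
| 20% / 30% | 33.3% v 52.3% | 26.7% v 36.6% | 43.8% |
| 30% / 20% | 33.3% v 52.3% | 23.3% v 41.9% | 93.3% |
| 20% / 30% | both 33.3% | 26.7% v 23.3% | 8.3% |
| 22.5% / 27.5% | both 33.3% | 25.8% v 24.2% | 4.8% |
| 25% / 25% | both 33.3% | 25.0% v 25.0% | 3.7% |

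Fisher on observed cases with the 20% / 30% split (128 v 112) has 83.4% power, 82.8% with the split reversed, and rejects 4.2% when completer rates are equal.

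**The case against.** The strongest reply is that the comparison is in the plan. Section 2.18 is the statistical section, and its power text gives the endpoint by arm, the threshold, the time point, the test, alpha and the number per arm. StatXact is listed as a tool, which fits an exact test. A general mixed-model strategy for longitudinal measures can coexist with an exact test of one binary outcome, and sizing on 120 of 160 points to observed cases.

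Much of this stands. A reader might infer that the plan contains no test of its primary endpoint at all. The documents do not support that, because Fisher's test is tied to this endpoint. What remains is that Fisher's test is given only as the basis of the power estimates, while another analysis carries the word primary. The Hypothesis 3 reference to other outcome measures neither names the proportion nor specifies a model for a binary outcome.

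A reader might also infer that the primary test is left open, because descriptive work will identify "missing data and patterns of attrition that will guide decisions about the use of transformations and appropriate tests". That is a generic data-screening sentence and does not show it.

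Nor does the plan ignore missing data: it has intention-to-treat by arm, missing at random, a dropout comparison and a conditional adjustment. None of these classifies a participant on the binary endpoint.

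Finally, a reader might take the 8.3% as a general false-positive rate. It needs an assumed 10-point attrition imbalance and is an error only if the target is the difference among completers. If missing truly means not achieved, the rates of 26.7% and 23.3% do differ. At a 5-point imbalance the figure is 4.8%.

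**Conclusion.** The point holds as a mismatch between the declared endpoint and the declared primary analysis, together with a missing classification rule. It should be fixed before analysis, because as written the plan would report a test of mean weight change as primary for a trial sized on a proportion. It is not an error in the sample size.

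The gap of 79.7% v 55.5% power at 3.8 lb rests on normality, equal SDs and carrying a shift in pounds over to percent loss. The 81.8% v 74.8% contrast rests on the plan's own attrition, taken as equal in both arms, and a newsletter rate of exactly one-third. The unequal-attrition figures show sensitivity only and predict nothing about this trial.

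**What to change.** In the Hypothesis 3 Analysis Plan of section 2.18:

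- **Name one primary analysis.** Loss of at least 5% from baseline at month 12 (yes/no), compared between randomized arms in all randomized participants, two-sided alpha 0.05, reported as a risk difference with 95% confidence interval.
- **State one missing-status rule.** A suitable choice is multiple imputation of month-12 percent weight change within arm, using month-4 percent change and the randomization stratum. Yes/no status is then derived in each imputed data set and the risk difference pooled by Rubin's rules. Give complete-case Fisher's exact test and missing = not achieved as sensitivity analyses.
- **Label the rest.** Call the mixed models of mean weight change and all 24-month results secondary, both there and in the opening of section 2.18.
- **Align the power text** in sections 2.18 and 3.12 with the named test and denominator.

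The essential correction is that the primary test and the missing-status rule match the declared endpoint; the imputation method is one sound way to do it. A Mantel-Haenszel comparison stratified by the 3.5% weight-loss category is an optional efficiency gain. If the stratum is used, state how a loss of exactly 3.5% and a missing month-4 weight are assigned, since sections 2.3 and 2.18 define only below and above 3.5%.

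The cost is wording, one imputation step and a revised power statement in two places. Weight is already scheduled at months 0, 4 and 12. The downside is reliance on missing at random, which the sensitivity analyses address.

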3.1 What is the age range of the subject population?

64-82

3.2 What is their gender?

* Both males and females

Provide a justification if single gender selected:

3.3 Will any racial or ethnic subgroups be explicitly excluded from participation?

* No

If **Yes**, identify subgroups and provide a justification:

3.4 For studies conducted in the U.S., do you expect that all subjects will be able to comprehend English?

* Yes

[\[reviewer notes-\]](#)

3.5 Participation of Children: Will children less than 18 years of age be studied?

* No

If **No**, provide a justification for excluding children:
This is a study of Medicare eligible retirees

[\[reviewer notes-\]](#)

3.6 Does this research study involve prisoners, or is it anticipated that the research study may involve prisoners?

* No

[\[reviewer notes-\]](#)

3.7 Will pregnant women be knowingly and purposely included in this research study?

* No

[\[reviewer notes-\]](#)

3.8 Does this research study involve neonates of uncertain viability or nonviable neonates?

* No

[\[reviewer notes-\]](#)**3.9 Fetal Tissues: Does this research involve the use of fetal tissues or organs?**

* No

[\[reviewer notes-\]](#)

--->

3.10 What is the total number of subjects to be studied at this site, including subjects to be screened for eligibility?

Note: The number below is calculated by summing the data entered in question 3.11. Any additions or changes to the values entered in 3.11 will be reflected in 3.10.

* 1500

3.11 Identify each of the disease or condition specific subgroups (include healthy volunteers, if applicable) that will be studied.

Click on the "Add" button and specify for each subgroup:

1) how many subjects will undergo research related procedures at this site; and

2) if applicable, how many subjects will be required to undergo screening procedures (e.g., blood work, EKG, x-rays, etc.) to establish eligibility. **Do Not include subjects who will undergo preliminary telephone screening.**

*

	Subgroup	Number to undergo research procedures	Number to undergo screening procedures
View	Enrolled in GLB 12 session	320	1500

3.12 Provide a statistical justification for the total number of subjects to be enrolled into this research study at the multicenter sites or this site.

* If applicable, refer to the statistical section in the protocol or grant. Specify the page numbers in the textbox.

Power and Sample Size Considerations: The primary endpoint of this investigation is defined as the proportion of participants, in each intervention arm, who maintain the designated target weight loss of $\geq 5\%$ at 12 months from baseline. Additional power calculations were derived for the changes in absolute weight loss from 0-12 months and in fasting glucose levels from 0-12 months. For our primary endpoint of $\geq 5\%$ weight loss at 12 months, with $N = 160$ in each arm and assuming no more than 25% attrition, we have 80% power to detect differences of 19% between the two intervention conditions in the proportion of subjects achieving this weight loss target. There is 90% power to detect differences of 21% between the two groups. This translates to roughly half or more of the participants in the telephonic continued contact group maintaining $\geq 5\%$ weight loss compared to only about one-third of those in the newsletter control condition. These estimates are based on a Fisher's Exact test conducted at $\alpha = 0.05$ two sided with $N = 120$ in each arm.

[\[reviewer notes-\]](#)**3.13 Inclusion Criteria: List the specific criteria for inclusion of potential subjects.**

Study Inclusion Criteria.

Non-diabetic, Medicare eligible men and women, ages 65-80 (by 1/1/13), with a BMI ≥ 27 and at least one of the following additional risk factors will be included. Eligible participants

must reside in the Western PA or Tri-State region at least half the year and be available to attend the 12 in-person sessions at a location closest to their residence. In addition, eligible participants must meet the following criteria:

EITHER a score of 15 or greater on the ADA risk test,

OR one of the following:

- 1) Large waist circumference (> 40 inches men, >35 inches women);
- 2) hypertension or taking hypertension medication;
- 3) physician confirmed low HDL level (<40 mg/dL men, < 50 mg/dL women);
- 4) physician confirmed elevated triglyceride level \geq 150 mg/dL;
- 5) physician confirmed fasting glucose \geq 100 mg/dL and < 126 mg/DL

The eligibility criterion of BMI \geq 27 has been selected (as opposed to BMI \geq 25, a standard overweight cut point) in order to insure that the selected participants are indeed at higher risk for diabetes (1) and to insure that elderly women at a BMI of 25 will not be at increased risk for bone loss and/or muscle loss with weight reduction.

Finally, study participants must have access to a telephone (including appropriate assistive devices if they have hearing impairments), and be able to read at the 6th grade level.

Eligible individuals are those who meet the following criteria:

1. Overweight or obese (BMI of \geq 27 kg/m²)
2. Do not currently have a diagnosis of diabetes
3. Are between the ages of 65-80 as of January 1, 2013
4. Documented evidence of at least one additional health risk factor for diabetes including EITHER
 - a) a score of 15 on the ADA risk screening test, OR
 - b) one of the following: history of hypertension or currently taking hypertensive medications; large waist circumference (> 40 inches men, > 35 inches women); physician confirmed low HDL level (<40 mg/dL men, <50 mg/dL women); physician confirmed high fasting glucose level (\geq 100 mg/DL and < 126 mg/DL); physician confirmed high triglyceride level (\geq 150 mg/DL)

Individuals who meet the above criteria will be invited to complete the informed consent procedure and will be scheduled for a baseline assessment (it is anticipated that it will take approximately 1-3 months to complete these procedures prior to the baseline assessment and the first GLB session).

3.14 Exclusion Criteria: List the specific criteria for exclusion of potential subjects from participation.

Study Exclusion Criteria.

- 1) prior diagnosis of diabetes or currently using medicines used to treat diabetes;
- 2) unable to provide physician (or other health care provider) referral/ clearance for exercise participation;
- 3) a weight loss of 4.5 kgs or more in the past six months (to rule out unintentional weight loss that may be an indicator of current or incipient physical illness);
- 4) current use of weight loss medications;
- 5) unable to attend at least 75% of the GLB 12-session program
- 6) unwilling to self-monitor food, activity and weight as prescribed
- 7) participants who have had bariatric surgery will be excluded if at the time of study enrollment they are less than 2 years status/post surgery (this is the period in which individuals are likely to have had the maximum amount of weight loss and some will begin to experience weight regain). Individuals who are greater than 2 years status/post bariatric surgery may be considered for inclusion as long as they have not had a weight loss of greater than 4.5kgs in the past six months.

Excluded individuals will be referred to other resources as appropriate.

3.15 Will HIV serostatus be evaluated specifically for the purpose of participation in this research study?

* No

[\[reviewer notes-\]](#)**4.1** Select all recruitment methods to be used to identify potential subjects:

Advertisements

Recruitment Letters and/or Scripts

Research Registry

[Pitt + Me](#)

Other Strategies: Described below

Advertisements

Upload the advertisements for review:

Name	Modified Date
10-4-12 [name] Letter and Eligibility Checklist-revised.docx	10/4/2012 8:13 PM
10-1-12 [name] Letter and Eligibility Checklist.docx	10/4/2012 8:00 PM
PowerPoint for In Person Screening Events	11/12/2012 9:37 PM
Letter to participants-outline of next steps-PRS- describe locations.docx	1/18/2013 11:18 AM

Recruitment Letters and Scripts

Upload recruitment letters/scripts/text:

Name	Modified Date
GLB Written Screening Consent	5/14/2012 7:52 PM
ADA Risk Screening Test	5/14/2012 7:55 PM

Research Registry

List the IRB approval number and title for each registry source:

<http://www.pepper.pitt.edu/>

The Pittsburgh Claude D. Pepper Older Americans Independence Center ([name]) The Center for Research on Health and Care, Graduate School of Public Health, University of Pittsburgh). The IRB approval number for this registry is IRB0503150.

[name], a Co-Investigator with the Pitt Retiree Study, introduced us to [name] and we made a formal application to use the Registry. We were approved by the Executive Committee and have received permission to access the database/ mailing list. Letters were generated and sent to registry participants in the same way as was done with the University of Pittsburgh retiree database (based on age and zipcode).

4.2**Provide a detailed description of your recruitment methods, including identifying and initiating contact with participants:**

As a community translational research study targeting individuals who had been previously employed at either the main campus or the four branch campuses of the University of Pittsburgh, all procedures will be coordinated through the University Human Resources (HR)

benefits department utilizing 2 (FTE) project assistants under the supervision of the PI and the Program Coordinator. All screening and recruitment procedures are being designed to meet with the approval of [name], Director of Benefits. [name] (and the HR database) indicate that many of these individuals remain in the Western PA region.

Annual preparations for screening and recruitment for the GLB-12 session intervention will commence in September 2012 for years 1, 2, and 3 of the study prior to the benefits elections deadline in early December. We will target these retirees through mass mailings, benefits counseling sessions, and/or Medicare benefits screening fairs that are held for this group. The screening and recruitment activities will take place either by phone (in association with the mass mailings) or in person (using existing benefits events).

A letter and/or flyer describing the Group Lifestyle Balance (GLB) program along with the 7-question American Diabetes Association risk screening test (a form commonly used at community health screenings to raise awareness, see uploaded attachments) will be utilized. Once subjects are screened and eligible they will be invited to complete the informed consent procedures and schedule baseline assessments

In addition we have added community based screening methods to meet recruitment targets:

1. Claude Pepper Registry (as above)
2. Outreach to other community facilities where there may be networks of 65-80 year olds interested in participation (e.g., church based programs, senior centers, recreational facilities, municipal and borough facilities associated with programs for older adults).

Note: Questions jump from 4.2 to 4.6 as questions 4.3-4.5 have been removed and the information is now captured in 4.1

[\[reviewer notes→\]](#)

4.6 Are you requesting a waiver to document informed consent for any or all participants, for any or all procedures? (e.g., a verbal or computerized consent script will be used, but the subjects will not be required to sign a written informed consent document. *This is not a waiver to obtain consent.*

* Yes

4.6.1 Identify the specific research procedures and/or the specific subject populations for which you are requesting a waiver of the requirement to obtain a signed consent form.

Addressed below:

If not all, identify the specific procedures and/or subject populations for which you are requesting a waiver:

In some, but not all, cases screening will occur completely by phone and the participants will be determined to be eligible (with the exception of the height and weight confirmation, in person, to determine BMI status). In those cases where subjects appear to meet all of the eligibility criteria they may be invited directly to sign informed consent and proceed with baseline research assessments at the first and only in person contact prior to the start of intervention.

4.6.2 Indicate which of the following regulatory criteria is applicable to your request for a waiver of the requirement to obtain a signed consent form.

45 CFR 46.117(c)(2)

45 CFR 46.117(c)(1) That the only record linking the subject and the research would be the consent document and the principal risk would be potential harm resulting from a breach of confidentiality. Each subject will be asked whether the subject wants documentation linking the subject with the research, and the subject's wishes will govern; or

45 CFR 46.117(c)(2) That the research presents no more than minimal risk of harm to subjects and involves no procedures for which written consent is normally required outside of the research context.

4.6.2.1

Address why the specific research procedures for which you are requesting a waiver of the requirement to obtain a signed consent form present no more than minimal risk of harm to the research subjects:

These are procedures that are typically done at health screens and benefits fairs that present only minimal risk to subjects

4.6.2.2

Justify why the research listed in 4.6.1 involves no procedures for which written informed consent is normally required outside of the research context:

These are procedures that are typically done at health screens and benefits fairs that present only minimal risk to subjects

4.6.3

Address the procedures that will be used and the information that will be provided (i.e., script) in obtaining and documenting the subjects' verbal informed consent for study participation:

See the Script and Screening Interview attached

Upload Scripts:

Name	Modified Date
ADA Risk Screen	5/14/2012 8:33 PM
Script for Screening Interview and Verbal Consent	5/14/2012 8:33 PM

[\[reviewer notes-\]](#)

4.7 Are you requesting a waiver to obtain informed consent or an alteration of the informed consent process for any of the following?

* No

4.7.1 If Yes, select the reason(s) for your request:

There are no items to display

General Requirements: The Federal Policy **[45 CFR 46.116 (d)]** specifies in order for a waiver of consent to be approved, the request must meet four criteria. For each request, you will be asked to provide a justification addressing how each of these criterion is met.

[\[reviewer notes-\]](#)

4.8 Are you requesting an exception to the requirement to obtain informed consent for research involving the evaluation of an 'emergency' procedure?

Note: This exception allows research on life-threatening conditions for which available treatments are unproven or unsatisfactory and where it is not possible to obtain informed consent.

* No

[\[reviewer notes-\]](#)**4.9****Upload all consent documents for watermarking:**

Draft Consent Forms for editing:

Name	Modified Date
Final Revised Consent for Participation in a Research Study-May 22.docx	1/16/2014 9:24 AM

Approved Consent Form(s):
Name Modified Date

[\[reviewer notes-\]](#)**4.10****Will all potential adult subjects be capable of providing direct consent for study participation?**

*
Yes

[\[reviewer notes-\]](#)**4.11****At what point will you obtain the informed consent of potential research subjects or their authorized representative?**

Prior to performing any of the research interventions/interactions

4.11.2**Taking into account the nature of the study and subject population, indicate how the research team will ensure that subjects have sufficient time to decide whether to participate in this study. In addition, describe the steps that will be taken to minimize the possibility of coercion or undue influence.**

We will be marketing obesity management/diabetes prevention programs to retirees during the Medicare open enrollment benefits selection period. Essential operational procedures are already in place (marketing materials, mass mailing schedules, "Welcome to Medicare" benefits fairs and health screening events) and this is a naturally occurring annual cycle. Thus, what we will be offering (GLB intervention) may be viewed as complimentary to what these individuals are already seeking (health care) and participation is completely voluntary.

Using this natural infrastructure as a platform for health dissemination efforts will enhance sustainability and magnify public health impact. However, we will make it clear to individuals that there is no obligation to participate in the GLB program and choosing not to do so will in no way affect their other retirement or medical benefits choices.

